4.2 SUBJECT DISPOSITION

Subject disposition will be summarized by treatment group and by all randomized subjects.

The summary will include

- number of subjects randomized
- number of subjects completed the study
- number of subjects discontinued from the study.

Reasons for discontinuation will be summarized by randomized treatment group for all randomized subjects. Table 4.2.1 provides the subject disposition for all randomized subjects.

Listing 4.2.1 provides subject disposition for all randomized subjects.

4.3 DEMOGRAPHICS AND BASELINE CHARACTERISTICS

Subject demographic and baseline characteristics data will be summarized by treatment group.

Demographic/baseline variables include sex, race, ethnicity, age, baseline height, baseline weight, and medical history. Tables 4.3.1, 4.3.2, and 4.3.3 will provide tabular summaries of the demographic and baseline variables for the safety, ITT, and restricted ITT populations, except for medical history, which will be summarized for the safety population only (Table 4.3.4).

Listing 4.3.1 provides sex, race, ethnicity, age, baseline height, baseline weight for all randomized subjects. Listing 4.3.2 provides medical history for all randomized subjects.

4.4 TREATMENT COMPLIANCE AND EXPOSURE

Records of SM and doses administered will be kept during the study. The Clinical Research Associates (CRAs) will review drug accountability during investigational site visits and at the completion of the study.

Duration of treatment exposure to SM will be summarized by treatment group for the safety population using descriptive statistics. Summaries of exposure will be provided separately for the Titration Period, Maintenance Period, and combined Titration and Maintenance Periods (Table 4.4.1).

For subjects randomized to Treatment 4, the number and percentage of subjects maintained on the target dose versus those reduced in dose (to Treatment 3 level) during the Maintenance Period will be provided (Table 4.4.2).

4.5 POTENTIAL EXCLUSIONS FROM ITT POPULATION

Study data will be examined during the Data Review (described below in section 4.6) for potential exclusions from ITT population. ICH E9 guideline outlines circumstances where it will usually be acceptable to omit subjects from the ITT population without causing bias. Some of the potential exclusions in this study are:

- Subjects who violate the inclusion/exclusion criteria;
- Subjects who fail to take at least one dose of study medication;

- Subjects who do not provide any post-baseline data;
- Enrollment of a subject who did not meet all inclusion/exclusion criteria which would affect subject safety or would negatively impact data integrity;
- Use of any prohibited concomitant medication that may confound study results;
- Subject dosing error that results in a serious adverse event;
- Having any non-compliance issues raised by the investigator or sponsor prior to breaking the blind;
- Study visit or procedure conducted outside of required time frame that may negatively affect subject safety;
- Subject visit/procedure falls outside of the window of time indicated by the protocol resulting in increased potential for risk to the subject or any damage to the integrity or completeness of the data.

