4.1 ANALYSIS POPULATIONS

The enrolled population consists of all subjects with ICFs signed by their parent or LAR (and IAFs signed by the subjects, where applicable).

The safety population consists of all randomized subjects who receive at least 1 dose of SM.

The intent-to-treat (ITT) population consists of all safety population subjects with at least 1 post-baseline efficacy assessment.

The restricted ITT population consists of all ITT population subjects with at least 1 efficacy assessment during the Maintenance Period.

The PK population consists of safety population subjects with at least 1 PK measurement.

The safety, ITT, restricted ITT, and PK populations are based on actual treatment received. Table 4.1.1 provides these analysis populations for all randomized subjects.

Listing 4.1.1 provides inclusion and exclusion criteria violations for all randomized subjects. Listing 4.1.2 gives analysis populations.

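### SAP 4.5 lets the data review remove subjects from the ITT population of 4.1 for post-randomisation events, and no efficacy table shows results without those removals

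*SAP*

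**What the plan says.** SAP 4.1 gives the definition: "The intent-to-treat (ITT) population consists of all safety population subjects with at least 1 post-baseline efficacy assessment". It has no exclusion clause and no reference to 4.5. The second efficacy set is nested in the first: "The restricted ITT population consists of all ITT population subjects with at least 1 efficacy assessment during the Maintenance Period".

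SAP 4.5 then describes potential exclusions from this ITT population, to be examined at the data review. It cites ICH E9 on when omitting subjects is usually acceptable, and introduces its list with "Some of the potential exclusions in this study are". The grounds include:

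- adherence problems, with no threshold given: "Having any non-compliance issues raised by the investigator or sponsor prior to breaking the blind"
- taking a disallowed drug, where the test is possible confounding: "Use of any prohibited concomitant medication that may confound study results"
- an error in dosing that leads to an SAE
- visits or procedures outside their window, in one bullet qualified as "resulting in increased potential for risk to the subject or any damage to the integrity or completeness of the data"

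SAP 4.6 leaves the final population definitions, and who is in or out, to that review. It takes place before database lock and is recorded in signed minutes.

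SAP 5.1.2 restricts treatment comparisons to ITT. SAP 5.2.2 (Table 5.2.2.1) and the ANCOVA in 5.5 (Table 5.5.1) use ITT, and Table 5.2.2.2 uses restricted ITT.

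**The concern.** A subject can meet the 4.1 definition in full and still be taken out of ITT under 4.5. Two programmers, one working from 4.1 and one from 4.5, could build different ITT sets.

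Non-compliance, use of a prohibited drug and missed visit windows all arise after randomisation and may be related to how a child responds or tolerates the dose. If they are, the adjacent-dose estimates and confidence intervals for the conduct problem subscale come from a selected set that is still labelled ITT.

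Opportunity for such flags also differs by arm. Post-randomisation visits run from 8 to 11 depending on treatment group, and the extra visits fall in titration, where the window is ±1 day.

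Treatments 2 and 3 each enter two of the three pairwise comparisons. Removing a poor responder from a middle arm improves that arm against one neighbour and equally against the other, so the two dose steps move in opposite directions and the apparent dose-response can change shape.

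**Working it through.** **Step 1. Sort the nine bullets of 4.5.**

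- Two (no dose taken, no post-baseline data) largely repeat 4.1.
- Two concern eligibility.
- Five concern events that can occur after randomisation: prohibited medication, a dosing error with an SAE, non-compliance, and two on visit timing.

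Some of the five have an objective core. Visit windows are numeric (±1 to ±3 days in the visit schedule), the dosing-error ground is event-based, and prohibited drugs may be listed in the protocol. The non-compliance ground has no threshold. The qualifiers about confounding and about damage to data integrity have no criterion.

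**Step 2. Look for an efficacy output free of the removals.**

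| Output | Population | Shows the unreduced 4.1 set? |
|---|---|---|
| Table 5.2.2.1, primary efficacy variable | ITT | No |
| Table 5.2.2.2, summary statistics | Restricted ITT (subset) | No |
| Table 5.5.1, ANCOVA | ITT; changes the model only | No |
| 5.3 and 5.4 tables | ITT or restricted ITT | No |
| 5.1.6 subgroup summaries | ITT | No |
| Listing 5.2.2.1 | ITT | No |
| Table 4.1.1, Listing 4.1.2, minutes | Membership only | Who was removed, not the effect |

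**Step 3. Check the plan's numbers.** From 3.2, 72 × (1 − 0.17) = 59.76, which agrees with the stated 60 completers. From 3.3, allocation is 1:1:1:1, so 72/4 = 18 per arm and 1/18 = 5.6%. The SAP gives no SD, effect size or expected number of removals.

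**Step 4. Size, by simulation.** Assumptions: two arms of 18, standard normal changes (higher = worse), no true difference, removals from one arm only, 100,000 replicates per cell, Monte Carlo SE 0.001. With no removals the mean Hodges-Lehmann difference is 0.000 and its sampling SD is 0.345.

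| How subjects are removed | 1 removed (SD) | 2 removed (SD) |
|---|---|---|
| At random | 0.000 | −0.001 |
| Ranked by a score correlated 0.3 with poor response | −0.032 | −0.059 |
| Ranked by a score correlated 0.5 | −0.052 | −0.098 |
| Drawn from the worse half | −0.050 | −0.105 |
| Exactly the worst responders (constructed extreme) | −0.088 | −0.173 |

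Against the standard error, correlated removals run from 0.032/0.345 = 0.09 to 0.098/0.345 = 0.28, and the extreme is 0.173/0.345 = 0.50. In that extreme the average exact 95% interval (20,000 replicates) moves from (−0.70, 0.70) to (−0.77, 0.58) for one removal and (−0.85, 0.50) for two.

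A separate simulation of 10,000 runs gave extreme-case shifts of 0.10 and 0.18 SD. The two-sided Wilcoxon rejection rate at 0.05 was about 6.9% and 8.9%, against 4.75% with no removal; random removals left it near 5%.

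**The case against.** The best defence is that 4.5 directs no removal. It lists potential exclusions, refers to ICH E9 circumstances in which omission should not cause bias, and hands the decision to a documented pre-lock review. On that reading 4.1 is a base definition that 4.6 completes. This softens the contradiction but does not remove it: stating a no-bias aim does not make a response-related removal unbiased, and an undefined non-compliance ground gives the review nothing to test against that aim.

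SAP 5.1.7 might be cited as confirming 4.1, since it leaves out discontinuers without post-randomisation scores and carries others forward by LOCF. It is a missing-data rule and does not address deviations, so it is consistent with 4.1 but adds little.

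Transparency deserves credit. "Table 4.1.1 provides these analysis populations for all randomized subjects", baseline tables are planned for the safety, ITT and restricted ITT sets (4.3), and section 4 promises listings of all CRF data. A reader could see who was removed and compare baselines. None of these is an efficacy result without the removals, and the conduct problem listing is itself limited to ITT.

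The impact is modest, and that stands. Efficacy is a secondary objective, p-values are descriptive, the sample size has no statistical basis, and the safety population serving the primary objective is unaffected. This limits the severity. Selection still affects the estimates and intervals, and 5.1.2 uses these comparisons to judge dose-response.

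**Conclusion.** The concern holds. SAP 4.1 and 4.5 give different answers on who belongs to ITT, the grounds in 4.5 are open-ended and partly undefined, and no planned efficacy table allows the effect of removals to be seen.

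For one or two removals in one arm of 18, the bias ranges from nil (random) through 0.03 to 0.10 SD (correlation 0.3 to 0.5 with poor response) to 0.09 or 0.17 SD in a constructed extreme, at most half a standard error. This rests on normal changes, no true difference and one-sided removal; the number and direction of any actual removals are unknown. It should be fixed, but it does not threaten the primary safety objective.

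**What to change.** 1. State that ITT is exactly as defined in 4.1 for all main efficacy analyses, and that 4.5 cannot remove subjects from it for post-randomisation deviations.
2. Use those deviations only to define a named per-protocol set, with objective criteria fixed before the data review, above all for non-compliance and for medication that might confound. Run Table 5.2.2.1 once on that set as a sensitivity analysis.
3. Allow exclusion for eligibility violations only on pre-randomisation information, applied in the same way to all arms.
4. Confine the population part of the 4.6 review to applying these definitions.

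As a caution only: the non-compliance ground relies on timing relative to unblinding, yet the design description in SAP 3.1 states no masking. Check that wording against the protocol.

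The cost is SAP wording, one extra table, and a few non-adherent subjects kept in the main analysis.

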4.6 DATA REVIEW

The checking and assessment of data to revisit the proposed methods of statistical analysis for the purpose of finalizing the planned analysis prior to the database lock will be conducted. The following lists some of the aspects of analysis that would be considered:

- Checking of data for potential exclusions from ITT population;
- Precise definitions of analysis populations, especially which subjects will be included and which will be excluded;
- Handling of missing data;
- Pooling of centers;
- Outlier identification and specific decisions taken on how these will be handled.

The data review will be documented in agreed and signed meeting minutes, which will include a version of Listing 4.1.2 as appendix. The data review will be included in Appendix 13.1.

5. EFFICACY ANALYSES

5.1 GENERAL CONSIDERATIONS AND STATISTICAL/ANALYTICAL ISSUES

5.1.1 Definition of Baseline

Unless stated otherwise, the first Titration Period visit will be considered as Baseline for statistical analyses. For calculation of changes from baseline, the last available measurement/assessment before the first study drug application will be used as Baseline measure.

5.1.2 Treatment Comparisons

Statistical testing to compare treatment groups (overall and pairwise) will be performed for the ITT population only using appropriate statistical methods, as described in the efficacy subsections below. Dose-response relationship will be assessed based on a review of the results of the complete set of pairwise comparisons of Treatment 1 vs. Treatment 2, Treatment 2 vs. Treatment 3, and Treatment 3 vs. Treatment 4, without adjustment for

multiple testing. Given the small per-treatment group sample size for the study, the resulting p-values from the statistical testing will be used for descriptive purposes only (i.e., not for inferential purposes), primarily as an aid in the clinical interpretation of the efficacy results.

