3. DESIGN OF THE STUDY

3.1 STUDY DESIGN

This will be a randomized, multicenter, parallel group, dose-ranging safety and tolerability study in children with ADHD and persistent serious conduct problems. The target subjects are healthy male or female children aged 6 to 12 years, inclusive, with a diagnosis of ADHD with persistent serious conduct problems. To determine eligibility for the study, subjects will undergo an initial screening visit. Seventy-two subjects will be randomized in the study; assuming a 17% dropout rate, it is anticipated that 60 subjects will complete the study.

[figure not shown]
The study will consist of a Screening Period (within 28 days prior to the first dose administration), a Titration Period of 2 to 5 weeks, a Maintenance Period of 6 weeks, and a Safety Follow-up, which will be performed 30 days after the final study visit. The total subject duration in the study will be 16 to 19 weeks depending on the treatment group assignment. The total study duration is anticipated to be 15.5 months.

A total of 72 subjects will be randomized based on weight at baseline, to 1 of 4 treatment groups. A dose titration schedule will be followed (Table 1), where dosing for subjects < 30kg will be initiated at 1.67mg/day and dosing for subjects \geq 30kg or more will be initiated at 3.34mg/day. The titration schedule will be followed until the target dose (Treatment 1, 2, 3, or 4) is reached. Subjects will remain at the target dose for 6 weeks.

Table 1. Dose Titration Schedules (mg/day)

Week	1	2	3	4	5	6
Treatment Weight	Titration	Titration	Titration or Treatment 1	Titration or Treatment 2	Titration or Treatment 3	Treatment 4
< 30kg	1.67 (1.67mg qhs)	3.34 (1.67mg bid)	5 (1.67mg tid)	10 (3.33mg tid)	15 (5mg tid)	20 (6.67mg tid)
≥ 30kg	3.34 (1.67mg bid)	5 (1.67mg tid)	10 (3.33mg tid)	20 (6.67mg tid)	30 (10mg tid)	40 (13.33mg tid)

A study schematic is presented below.

Following 2 weeks of titration, subjects randomized to Treatment 1 in each weight group will receive Maintenance Treatment 1 (5mg/day for children < 30kg and 10mg/day for children ≥ 30kg), while the remaining subjects will receive the same level of drug as a titration step to the next level (Maintenance Treatment 2: 10mg/day and 20mg/day) and so on until the final subjects in each weight group reach the highest doses (20mg/day and 40mg/day).

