3.1.2 Titration Period

Subjects who meet the requirements for study participation will proceed to the Titration Period. Randomization will occur at the first Titration Period visit (Baseline). Subjects $< 30\text{kg}$ will be assigned a 1.67mg/day dose (1 week) followed by a 3.34mg/day dose (1 week)

followed by maintenance dosing at 5mg/day or continued titration up to 10, 15 or 20mg/day. Subjects \geq 30kg or more will be assigned a 3.34mg/day dose (1 week) followed by a 5mg/day dose (1 week) followed by maintenance dosing at 10mg/day or continued titration up to 20, 30, or 40mg/day.

Baseline safety (including Simpson-Angus Scale [SAS], Barnes Akathisia Scale [BAS], Abnormal Involuntary Movement Scale [AIMS]) and efficacy assessments (including NCBRF-TIQ, Clinical Global Impression [CGI] and Swanson, Nolan and Pelham Rating Scale - Revised [SNAP-IV]) will be performed. Inclusion/Exclusion criteria should be re-assessed at this visit. Concomitant medication and AE information will be collected.

After the first Titration Period visit, subjects will return to the study site weekly for dose increases, monitoring of AEs, and the administration of safety and efficacy scales. Procedures to be performed are collection of vital signs and weight, and PK blood sampling (at Weeks 2 and 3). Assessments of concomitant medications and drug compliance will be performed.

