4. DATA ANALYSIS

Tabular summaries of the data collected during the study will be presented to provide a general description of the subjects studied and an overview of the efficacy and safety results. Data from all sites will be combined in the computation of these summaries, and summaries will be presented by treatment group. Within each treatment group, summaries will also be presented by weight category at baseline ($< 30\text{kg}$, $\geq 30\text{kg}$), where appropriate. All subjects randomized to Treatment 4, whether they are maintained on Treatment 4 or reduced to Treatment 3, will be analyzed under the Treatment 4 group. Continuous variables will be summarized using descriptive statistics (number of subjects, mean, standard deviation [SD], median, and minimum and maximum values). Categorical (nominal) variables will be summarized using frequency tables (number and percentage of subjects in each category). If some values are missing, the percentages will sum to less than 100%.

In addition to tabular summaries, subject data listings will be provided. All data collected on CRF and from central laboratory will be presented in data listings. Where appropriate, data will be summarized for each protocol-specified visit. Unscheduled data will be listed but not summarized.

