5.1.5 Multiple Comparisons/Multiplicity

Pairwise comparisons (Treatment 1 vs. Treatment 2, Treatment 2 vs. Treatment 3, and Treatment 3 vs. Treatment 4) will be performed but without adjustment for multiple comparisons.

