5.2.2 Results of Primary Efficacy Analysis

The changes from baseline in the NCBRF-TIQ conduct problem subscale scores at each post-baseline visit and endpoint will be compared among treatment groups using Kruskal-Wallis test (for the overall comparisons) and Wilcoxon rank-sum test (for the pairwise comparisons of Treatment 1 vs. Treatment 2, Treatment 2 vs. Treatment 3, and Treatment 3 vs. Treatment 4) for the ITT population. The Hodges-Lehmann estimators and associated 95% confidence intervals will be calculated for the median differences between Treatment 1 and Treatment 2, Treatment 2 and Treatment 3, and Treatment 3 and Treatment 4 (Hollander M, 1999). Table 5.2.2.1 provides the primary efficacy results for overall and pairwise comparisons for NCBRF-TIQ conduct problem subscale for the ITT population. Table 5.2.2.2 provides the summary statistics for NCBEF-TIQ conduct problem subscale for the restricted ITT population.

Listing 5.2.2.1 provides NCBRF-TIQ conduct problem subscale data for the ITT population.

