5.5 SENSITIVITY ANALYSIS

As a sensitivity analysis, the changes from baseline in the NCBRF-TIQ conduct problem subscale scores at each post-baseline visit and endpoint will be compared among treatment groups using analysis of covariance (ANCOVA) with treatment and weight group as the main factors and the baseline value as the covariate. Table 5.5.1 provides the sensitivity analysis results for NCBRF-TIQ conduct problem subscale for the ITT population.

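### Efficacy dose-response is judged from three adjacent-dose comparisons only; the SAP specifies no ordered analysis and no Treatment 4 minus Treatment 1 difference with an interval (minor)

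*SAP*

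**What the plan says.** Section 5.1.2 sets the method for dose-response: "Dose-response relationship will be assessed based on a review of the results of the complete set of pairwise comparisons". It lists three pairs, all adjacent. Section 5.1.5 repeats them: "Pairwise comparisons (Treatment 1 vs. Treatment 2, Treatment 2 vs. Treatment 3, and Treatment 3 vs. Treatment 4) will be performed", with no multiplicity adjustment. Section 5.1.2 also limits what the tests are for: "the resulting p-values from the statistical testing will be used for descriptive purposes only (i.e., not for inferential purposes".

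Section 5.2.2 applies this to the NCBRF-TIQ Conduct Problem score, with Kruskal-Wallis overall and Wilcoxon rank-sum for the three pairs. Hodges-Lehmann estimates with 95% CIs "will be calculated for the median differences between Treatment 1 and Treatment 2, Treatment 2 and Treatment 3, and Treatment 3 and Treatment 4". Sections 5.3 and 5.4 use the same template for every other efficacy variable. Section 5.5 adds an "analysis of covariance (ANCOVA) with treatment and weight group as the main factors and the baseline value as the covariate" but names no contrast.

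The arms are ordered. Table 1 in Section 3.1 gives maintenance doses of 5, 10, 15 and 20 mg/day below 30 kg. From 30 kg upward, Section 3.1.2 has two fixed weeks "followed by maintenance dosing at 10mg/day or continued titration up to 20, 30, or 40mg/day". Within each weight group the doses stand in the ratio 1:2:3:4.

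**The concern.** The three listed pairs are half of the six possible. They omit 1 vs 3, 2 vs 4 and, most importantly, 1 vs 4, where a gradual response would be largest. Kruskal-Wallis takes no account of dose order, and the ANCOVA treats treatment as an unordered factor.

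Because the p-values only aid interpretation, the displayed estimates and intervals carry the message. If the response rises gradually, each adjacent step is small relative to its error. The three estimates can then disagree in direction although the underlying gradient is steady. A reader could take three imprecise, inconsistent steps for a flat or erratic dose-response. The three reported intervals cannot be combined into one for Treatment 4 minus 1: neighbouring estimates share an arm, and Hodges-Lehmann estimates do not add exactly.

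**Working it through.** **Sample size.** Section 3.2 gives 72 randomized and 17% dropout: 72 × 0.83 = 59.8, which reproduces the stated 60 completers. With 1:1:1:1 allocation (Section 3.3) that is 72/4 = 18 randomized and 60/4 = 15 completing per arm.

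**Pairs.** Four arms give 4 × 3 / 2 = 6 pairs; three are specified.

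**Precision of one pair.** With a common SD, SE = SD × √(2/18) = 0.333 SD, whichever two arms are compared. The Hodges-Lehmann 95% CI half-width, by simulation, is about 0.70 SD.

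**Signal against error (assumed linear response, total Treatment 1-to-4 effect D in SD units).** An adjacent step is D/3, so step/SE = (D/3)/0.333 = D. Treatment 4 minus 1 is D, so its ratio is D/0.333 = 3D. An adjacent step is therefore no larger than its SE only when D is 1.0 or less. The normal-theory chance of a wrong sign is Φ(−D) for one adjacent pair and Φ(−3D) for Treatment 4 minus 1.

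**Chance that at least one of the three adjacent Hodges-Lehmann estimates has the wrong sign.** Simulated with 18 per arm and normal data. The integer case uses whole-point scores with an SD of 6 points, and an estimate of exactly zero is not counted as wrong.

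| Total effect D | One adjacent pair, Φ(−D) | Any of three, integer scores | Any of three, continuous | Treatment 4 minus 1, Φ(−3D) |
|---|---|---|---|---|
| 0.6 SD | 27% | 57% | 70% | 3.6% |
| 1.0 SD | 16% | 34% | 46% | 0.1% |
| 1.2 SD | 12% | 23% | 34% | <0.1% |
| 1.5 SD | 7% | 14% | 21% | <0.1% |

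The simulated columns are good to about one percentage point. The integer column is nearer the endpoint, which Section 3.5.1 defines as a sum of 14 item scores. With 15 per arm the continuous figures at 0.6 and 1.0 SD become 74% and 51%.

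**Other shapes (18 per arm, p<0.05, no weight or baseline effect).** The advantage of an ordered analysis depends on the shape:
- Single step of 1.0 SD between two neighbouring doses: any adjacent test 82–83%, weight-stratified Jonckheere-Terpstra 72–73%, ANCOVA linear contrast 78–80%.
- Fall at the top dose (0, 0.5, 1, 0.3 SD): 71%, 22% and 26%.
- Linear 1.0 SD: 43%, 85% and 88%.

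The adjacent figure has three chances to succeed; with no effect it reaches p<0.05 in 13.5% of trials, against 4–5% for either ordered analysis.

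**Time on treatment.** Section 3.1 has "a Titration Period of 2 to 5 weeks, a Maintenance Period of 6 weeks", with titration of 2, 3, 4 and 5 weeks for Treatments 1 to 4. Time at end of maintenance is therefore 8, 9, 10 and 11 weeks. A drift of 0.05 or 0.10 SD per week, with no dose effect, gives 3 × 0.05 = 0.15 or 3 × 0.10 = 0.30 SD for Treatment 4 minus 1. The stratified trend test then reaches p<0.05 in about 7% or 15%. An adjacent pair carries one week of drift, not three.

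**The case against.** The strongest reply is that this is preference. Adjacent comparisons answer a fair dose-ranging question, namely whether the next dose adds anything. The primary objective is safety and tolerability, the sample size has no statistical basis, and the p-values are descriptive. All of that stands. A reader might infer that the plan inflates an error rate or draws an invalid conclusion; it does neither, because no inferential claim is made.

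A reader might also infer that the gradient will be invisible. That is not supported: Section 4 provides means, SDs and medians per arm. An unadjusted Treatment 4 minus 1 interval could be built by hand from those, though it would be neither the planned Hodges-Lehmann estimate nor the adjusted one. Nor can one say the output will be absent from the tables, because Section 9 places the shells in separate documents. The point concerns the SAP text only.

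It is tempting to say that an adjacent step never exceeds its error, or that a trend analysis is always better. Both fail. The first needs a linear response with a total effect of at most 1.0 SD. The second reverses when the top dose falls off and, for the rank trend test, for a single step. Each planned estimate also comes with an interval, which warns the reader of its imprecision. These limits are why the additions should sit beside the planned comparisons and not replace them.

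The preference argument does not remove the point. Section 5.1.2 commits to assessing dose-response and names a method that leaves out the widest dose separation.

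**Conclusion.** The point holds as a minor, cheap improvement. The SAP text bases efficacy dose-response on three of six pairs, describes those three as complete, and specifies neither an ordered analysis nor a Treatment 4 minus 1 difference with an interval.

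Under a linear response with 18 per arm and integer scores, the planned display would include at least one wrong-direction step in roughly 14% to 57% of trials over total effects of 1.5 down to 0.6 SD. Treatment 4 minus 1 would point the wrong way in about 4% at 0.6 SD and about 0.1% or less from 1.0 SD upward. Effect size, SD, shape and score distribution are all assumptions, since the SAP states none.

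The missing estimate would not by itself establish a dose effect. There is no placebo arm, and time on treatment rises with dose group.

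**What to change.** Before database lock, amend Sections 5.1.2 and 5.2.2 for the change in NCBRF-TIQ Conduct Problem score at endpoint only:

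1. Add a linear dose-level contrast (−3, −1, 1, 3) in the Section 5.5 ANCOVA. It scores the treatment level and not mg/day, because the mg step differs between weight groups.
2. Add the Treatment 4 minus Treatment 1 difference with its 95% CI.
3. State that both are descriptive and stand alongside Kruskal-Wallis and the adjacent comparisons without replacing them.
4. Delete *complete set of* from Section 5.1.2.

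Footnote the outputs as follows:

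- (a) Time on treatment at end of maintenance rises from about 8 to 11 weeks across the dose groups, so without placebo a time trend cannot be separated from dose.
- (b) Section 5.1.7 uses LOCF and Section 4.1 admits subjects to ITT on one post-baseline assessment. Endpoint values of early dropouts may therefore come from titration, at a dose below the one assigned. Show both estimates in the restricted ITT population as well, without p-values, since Section 5.1.2 confines testing to ITT.
- (c) Treatment 4 subjects reduced to the Treatment 3 dose are analysed as Treatment 4. Section 4 says that such subjects, "whether they are maintained on Treatment 4 or reduced to Treatment 3, will be analyzed under the Treatment 4 group", while Section 4.1 bases the ITT population on treatment actually received. Reconcile the two first, because the Treatment 4 minus 1 difference is not well defined until then.

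The cost is SAP wording, two outputs for one variable at one time point, their restricted-ITT repeat and three footnotes; no new data. The downsides are low power for non-monotone shapes, and a Treatment 4 minus 1 difference that carries three weeks of any time drift against one for an adjacent pair.
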